3.2 INDEPENDENT REVIEW FACILITY

Not applicable to this study.

3.3 DATA MONITORING

There is no Independent Data Monitoring Committee (IDMC) planned for this study.

4. STATISTICAL METHODS

The analysis of this open-label study will be primarily based on descriptive statistical methods. Unless otherwise specified, no statistical tests are planned. Corresponding 95% Cls will be presented as appropriate.

For continuous variables, descriptive statistics (e.g., number of patients [n], mean, standard deviation [SD], median, 25th and 75th percentiles, minimum, maximum) will be calculated and summarized.

For categorical variables, the number and percentage in each category will be displayed.

The analyses outlined in this Statistical Analysis Plan (SAP) supersede those specified in the protocol.

4.1 ANALYSIS SETS

4.1.1 Full Analysis Set (Women)

The full analysis set of women (FASW) will include all enrolled pregnant who were exposed to ocrelizumab either 0-6 months before the LMP or in the first-trimester of pregnancy (i.e., up to gestational Week 13 [inclusive]). This corresponds to 13*7+6, 97 days, as the last day of the first trimester.

4.1.2 Full Analysis Set (Infants)

The full analysis set of infants (FASI) will include all infants born to women in the FASW who were potentially exposed to ocrelizumab during pregnancy.

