2.2 DETERMINATION OF SAMPLE SIZE

The study will include approximately 33 pregnant women.

There is no formal sample size calculation, as no confirmatory hypothesis testing is planned. The primary analysis will be descriptive. Considering a 10% dropout rate, approximately 30 evaluable infants are expected. A further investigation will be performed on the subgroup of infants whose mothers received the last dose of ocrelizumab 0-3 months before the LMP or during the first trimester

The precisions (width of the two-sided 95% confidence intervals [CIs] based on normal approximation) for different event rates (an "event" is defined as B-cell levels below lower limit of normal [LLN]) are shown in the following table. If no event is observed from the 30 infants during the study, there is a 95% confidence that the event rate is below 0.114.

Sample Size	Number of Events	Event Rate	Precision
30	1	0.033	0.165
30	2	0.067	0.195
30	3	0.100	0.222
30	4	0.133	0.244
30	5	0.167	0.262

 Table 1
 Sample Size Precision at Different Event Rates

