4.4.1 Primary Endpoint

The primary endpoint is binary, defined as the proportion in infants with B cell levels (CD19+ cells, absolute counts) below the LN), measured at Week 6 of life (Yes/No).

The primary estimand is defined as follows:

- Population: Infants exposed to commercial ocrelizumab up to 6 months before the woman's LMP or during the first trimester (up to gestational Week 13) of pregnancy and not exposed after the first trimester (FASI)
- Variable: Binary endpoint, based on whether the B cell level is below the age adjusted LLN.

- Treatment: Commercial ocrelizumab (potential exposure during pregnancy).
- Intercurrent events:
 - Withdrawal from the study prior to infant's Week 6 visit missing data will not be imputed
 - Interrupted pregnancy (elective/therapeutic abortion or stillbirth) missing data will not be imputed
 - Fetal complications, or other issues, that render the sample not suitable for measurement of B cell levels at week 6 of life. – missing data will not be imputed
 - Breastfeeding before sample at week 6 is taken:
 - \circ $\,$ No DMT postpartum whilst breastfeeding: B cell will be included
 - Received any DMT postpartum whilst breastfeeding: B cell will be excluded since sample will not be collected.
 - Resume OCR postpartum whilst breastfeeding: B cell will be included.
 - Infants that were born pre-term and whose interval of assessment was not adjusted (i.e. a baby was born at week 35, the blood sample needs to be taken at week 8 (±14 days), gestational weeks that would sum up to a full term baby): B cell will be included.
- Population-level summary: Proportion of infants with B cell below LLN and the two-sided 95% CI will be reported; no formal statistical testing will be done.

B-cell reference ranges by week of life (absolute and percentage counts) are defined by Borriello et al. 2022 (Appendix 4). B cell data being confounded with illness will be determined by clinical team in a blinded manner before conducting the primary analysis.

4.4.2 Analytical Approach for Primary Endpoint

The proportion of infants with B cell levels at Week 6 of life below the LLN will be analyzed using descriptive statistics. The event rate and corresponding Clopper Pearson 95% CI will be presented. A corresponding listing will be presented for B cell levels (absolute count), including whether any intercurrent events (ICEs) led to exclusion of infant data from the analysis.

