4.4.5 Subgroup Analyses for Primary Endpoint

To assess the impact of fetal exposure during pregnancy, a subgroup analysis will be performed of infants based on maternal OCR exposure prior to the study as list below:

- in 3-month interval of before/during pregnancy (3-6 months before the LMP, <3 months before the LMP, during the first trimester [up to gestational Week 13]
- ≥3 months before the LMP vs <3 months before the LMP and/or during pregnancy.

The analysis will be presented in the same way as for the primary endpoint

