4.8.1 Exposure of Study Medication

Ocrelizumab will not be administered post-baseline until the infant's birth. Treatment with commercial ocrelizumab may be resumed at any time after birth for women who decide not to breastfeed. Some women may decide to resume treatment with ocrelizumab whilst breastfeeding. For those women, treatment with ocrelizumab should be restarted after collection of the infant blood sample at Week 6 of life (±7 days) if possible, but the decision is left to the discretion of the woman and the investigator.

Definitions

Dose: Ocrelizumab dose is given as one infusion or two infusions administered 2 weeks apart. Women will be considered to have received a dose of treatment if at least part of one infusion of that Dose (either Day 1 or Day 15 for dual infusions) was given.

Treatment duration (in weeks) for woman received OCR will be calculated as follows: [(Date of last contact* - Date of first postpartum dose) + 1] / 7

*Earliest 1) date of last OCR dose plus risk window of 6 months (182 days)2) date of death3) Clinical Cut-off Date

Exposure Analysis

The following measures of exposure of ocrelizumab will be summarized in the SAFW using descriptive statistics:

- Number of patients completing each dose type (Dose 1, full dose; Dose 1 split dose #1; Dose 1, split dose #2, Dose 2, full dose; Dose 3, full dose)
- Treatment duration (weeks)
- Number of doses received (Day 1 and Day 15 infusions are considered as one dose)

• Total cumulative dose (mg)

A corresponding listing will be produced.

MS treatment postpartum

- Type of DMT including ocrelizumab use postpartum
- Time (months) between delivery and first postpartum ocrelizumab as continuous and categorical (0-3 months, >3 and ≤6 months, >6 months)
- Number of women who received ocrelizumab dose postpartum
- Number of ocrelizumab doses postpartum
- Time (months) between first and second postpartum ocrelizumab dose

4.8.2 Adverse Events

All summaries of AEs will be presented separately for women and infants based on the respective Safety population. Adverse events will be presented overall and by timepoint (defined below). AEs will also be presented for subgroups based on OCR exposure prior to the study as list below, for infants and women separately:

- In 3-month interval of before/during pregnancy (3-6 months before LMP, 0-3 months before to LMP, during the 1st trimester)
- ≥3 months before to LMP vs <3 months prior to LMP and/or during pregnancy

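### SAP 2.2 states precision by a score-type interval, but the planned Clopper-Pearson intervals will be 4% to 11% wider; the FASI wording in SAP 4.1.2 also needs tidying

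*SAP*

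**What the plan says.** **Precision.** SAP 2.2 expects about 30 evaluable infants from about 33 women after 10% dropout. It tabulates "The precisions (width of the two-sided 95% confidence intervals [CIs] based on normal approximation) for different event rates", with widths of 0.165, 0.195, 0.222, 0.244 and 0.262 for 1 to 5 events. It adds: "If no event is observed from the 30 infants during the study, there is a 95% confidence that the event rate is below 0.114". The same figures stand in SAP Appendix 1, in the protocol synopsis and in Protocol 6.1 (Table 5).

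**Planned interval.** SAP 4.4.2 states: "The event rate and corresponding Clopper Pearson 95% CI will be presented". SAP 4.4.1 calls the interval two-sided, and the protocol synopsis specifies a two-sided Clopper-Pearson interval.

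**Subgroup.** SAP 4.4.5 splits the primary endpoint by timing of the last maternal dose, including "≥3 months before the LMP vs <3 months before the LMP and/or during pregnancy", and says: "The analysis will be presented in the same way as for the primary endpoint". SAP 2 says only that some of the women should have potential fetal exposure. SAP 2.2 announces further investigation of that subgroup. Neither gives an expected number or a precision for it.

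**Analysis set.** SAP 4.1.2 says FASI "will include all infants born to women in the FASW who were potentially exposed to ocrelizumab during pregnancy". SAP 4.1.4 makes the infants' safety set (SAFI) the same as FASI. The primary estimand in SAP 4.4.1 labels as FASI the population "Infants exposed to commercial ocrelizumab up to 6 months before the woman's LMP or during the first trimester".

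**The concern.** A precision table in a descriptive study tells the reader how wide the reported interval will be. Here it is computed by one method and the result will be reported by another, wider one, so the table promises slightly more than the analysis will deliver. It also covers only the full cohort. A reader could carry the 30-infant figures over to the smaller subgroup with potential fetal exposure, where they do not apply.

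The wording of FASI is a separate and lesser matter. If its qualifier is equated with the narrower idea of potential fetal exposure (last dose under 3 months before the LMP or in the first trimester), infants of mothers last dosed 3 to 6 months before the LMP would leave FASI. Through SAP 4.1.4 they would also leave SAFI. Other sections of the SAP need those infants, so a programmer should not be left to choose.

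**Working it through.** **Inputs.** Number of infants: 33 × 0.9 = 29.7, about 30 (SAP 2.2). Stated bound 0.114 and five stated widths (SAP 2.2, Table 1). Planned method: two-sided 95% Clopper-Pearson (SAP 4.4.1 and 4.4.2, protocol synopsis).

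**Step 1: reproduce the plan's figures.** The plain Wald width, 2 × 1.96 × √(p(1−p)/30), does not match. The Wilson score interval has centre (p + z²/2n)/(1 + z²/n) and half-width z/(1 + z²/n) × √(p(1−p)/n + z²/4n²). With zero events its upper limit is z²/(n + z²) = 3.8415/33.8415 = 0.1135, which is the stated 0.114. Its widths match Table 1 for 2 to 5 events. For 1 event plain Wilson gives 0.1608. Replacing its lower limit by −ln(0.95)/30 gives 0.1650, which matches. All six stated figures are therefore Wilson-type score results.

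**Step 2: the planned method.** The Clopper-Pearson lower limit is the 0.025 quantile of Beta(x, n−x+1). The upper limit is the 0.975 quantile of Beta(x+1, n−x).

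| Events of 30 | Stated width | Wald | Wilson-type | Clopper-Pearson limits | Clopper-Pearson width | Excess over stated |
|---|---|---|---|---|---|---|
| 1 | 0.165 | 0.1285 | 0.1650 | 0.0008 to 0.1722 | 0.1713 | 0.006 (3.8%) |
| 2 | 0.195 | 0.1785 | 0.1948 | 0.0082 to 0.2207 | 0.2126 | 0.018 (9.0%) |
| 3 | 0.222 | 0.2147 | 0.2216 | 0.0211 to 0.2653 | 0.2442 | 0.022 (10.0%) |
| 4 | 0.244 | 0.2433 | 0.2437 | 0.0376 to 0.3072 | 0.2697 | 0.026 (10.5%) |
| 5 | 0.262 | 0.2667 | 0.2623 | 0.0564 to 0.3472 | 0.2908 | 0.029 (11.0%) |

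**Step 3: zero events.** The two-sided exact upper limit is 1 − 0.025^(1/n). For n = 30 it is 0.1157, against the stated 0.114. The one-sided exact 95% bound is 1 − 0.05^(1/30) = 0.0950.

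**Step 4: the subgroup.** The documents give no number, so n is assumed. The two-sided zero-event limit is 0.308 for n = 10, 0.218 for n = 15 and 0.168 for n = 20. These are about 2.7, 1.9 and 1.5 times the 30-infant limit of 0.116.

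**Step 5: FASI wording, sections side by side.** SAP 4.4.1 gives the label FASI to the whole cohort dosed from 6 months before the LMP through the first trimester. SAP 4.4.5 asks for a 3-to-6-month row of the primary endpoint. SAP 4.8.2 says "AEs will also be presented for subgroups based on OCR exposure prior to the study as list below, for infants and women separately", and its list has a 3-to-6-month row. Protocol 6 puts every infant of a mother in the women's FAS into the infants' safety population, without a qualifier. All of these fit a cohort-wide FASI. The qualifier in SAP 4.1.2 is the only part that can be read otherwise. Protocol 6 uses the same qualifier for its Infants' FAS.

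**The case against.** **The table is honestly labelled.** It says normal approximation, it is a planning aid, no hypothesis is tested, and the widths differ by only 0.006 to 0.029. This stands as far as it goes. Table 1 is not an arithmetic error, and no result will be wrong because of it. The mismatch with the planned interval remains.

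**The zero-event bound may be one-sided.** The sentence can be read that way. The exact one-sided bound is 0.095, and 0.114 would then be conservative. This stands too. The gap between 0.114 and 0.116 exists only against the planned two-sided interval and would not alone justify a change.

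**Subgroup precision is optional.** There is no formal sample size and no exposure quota, and every subgroup size above is an assumption. I agree: this is missing detail, not an error.

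**A stronger reading is tempting.** Protocol 3.3.2 calls women dosed 3 to 6 months before conception non-exposed. A reader might infer that the pooled primary proportion answers the wrong question by mixing these infants in. The documents do not support that. Protocol 2 opens by setting the scope as a last dose from 6 months before the LMP through the first trimester. The study title and the treatment line of the estimand use the potential-exposure phrase for that whole cohort. The narrower group has its own term, potential fetal exposure (SAP 2, Protocol 6.4.4), and SAP 4.4.5 already commits to a separate estimate for it by the primary method. Protocol 3.3.2 also counts from conception while the SAP rows count from the LMP, so the two groups do not coincide exactly.

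**A reader might also infer that infants will be lost from FASI and SAFI.** The sections in Step 5 show the opposite intent. It is a wording conflict, not a demonstrated loss.

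**Conclusion.** The point holds as a mismatch between planning and analysis methods. All five Table 1 widths are narrower than the planned two-sided Clopper-Pearson interval gives. The reported intervals will be 4% to 11% wider than stated, or 0.006 to 0.029 in absolute terms. The two-sided zero-event limit is 0.116 rather than 0.114, which is trivial. These results assume exactly 30 evaluable infants. Precision for the subgroup last dosed under 3 months before the LMP or in the first trimester will be lower, by an amount that depends on a number the documents do not give.

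The FASI qualifier is a minor wording conflict. The pooled estimand and the subgroup plan are not errors. No planned analysis or output changes. The correction is worth making because it is cheap and the figures are repeated in several places.

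**What to change.** 1. In SAP 2.2 and Table 1, and in the copy in SAP Appendix 1, replace the normal-approximation label with two-sided Clopper-Pearson. Restate the zero-event limit as 0.116 and the widths as 0.171, 0.213, 0.244, 0.270 and 0.291. Align the protocol synopsis and Protocol 6.1 at the next amendment. SAP 4 says that its analyses supersede those of the protocol, but that does not clearly cover sample-size text.
2. State in SAP 2.2 that these figures apply to the full cohort dosed from 6 months before the LMP through the first trimester, and that precision for the under-3-months/first-trimester subgroup in SAP 4.4.5 will be lower. Give 0.308, 0.218 and 0.168 as zero-event limits for an assumed 10, 15 and 20 infants, marked as illustrations.
3. In SAP 4.1.2 drop the qualifier, so that FASI is every infant born to a woman in the FASW. SAFI follows through SAP 4.1.4. This agrees with SAP 4.4.1, 4.4.5 and 4.8.2 and with the protocol's safety population. It does not match the protocol's definition of the Infants' FAS, which carries the same qualifier and can be aligned at the same amendment.

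The cost is text only: no new analysis, data or infants. The one downside is that the quoted precision becomes slightly less favourable.

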4.1.3 Safety Analysis Set (Women)

The safety analysis set of women (SAFW) will be the same as the FASW.

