6. STATISTICAL CONSIDERATIONS AND ANALYSIS PLAN

The analysis of this open-label study will be primarily based on descriptive statistical methods. Unless otherwise specified, no statistical tests are planned. Corresponding 95%CIs will be presented as appropriate.

The primary analysis will be performed after the last blood draw at Week 6 to examine B-cell levels in infants. The full analysis, including the analysis of growth velocity of the infants in the first year, will be conducted at the end of the study.

Full details of all statistical aspects and planned statistical analyses will be specified in a separate statistical analysis plan (SAP), which will be finalized prior to the locking of the study database and may include further exploratory analyses not explicitly described in this section.

Analysis Populations

Full analysis set (FAS)

Two separate FAS populations will be considered:

- Women's FAS: this will include all pregnant women defined through the inclusion and exclusion criteria in the study who were exposed to ocrelizumab either 0–6 months before the last menstrual period or in the first trimester of pregnancy (i.e., up to gestational Week 13 [inclusive]).
- Infants' FAS: includes all infants born to women in the FAS who were potentially exposed to ocrelizumab during pregnancy.

Safety Population

The safety population for the women is the same as the FAS. The safety population for infants will include all infants of mothers in the FAS population.

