4.1.4 Safety Analysis Set (Infants)

The safety analysis set of infants (SAFI) will be the same as the FASI.

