4.2 ANALYSIS OF STUDY CONDUCT

Patient disposition information will be summarized separately for the mother and infant as: the reason and number of screen failures (women only), the number enrolled, in the respective full analysis set (FAS) population, in the respective safety analysis set (SAF) population, completed each study period, discontinued from each study period and the reasons for discontinuation.

Major protocol deviations, including deviations of inclusion/exclusion criteria, will also be summarized and listed.

Mothers and infants enrolled but excluded from the respective FAS will be listed.

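### The SAP safety sets copy the exposure-window full analysis sets, so an enrolled woman with no in-window dose and her infant leave every AE summary table, and an infant exposed after Week 13 may leave too

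*SAP*

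**What the plan says.** SAP 4.1.1 defines the women's full analysis set (FASW), which "will include all enrolled pregnant who were exposed to ocrelizumab either 0-6 months before the LMP or in the first-trimester of pregnancy". It fixes the upper bound: "This corresponds to 13*7+6, 97 days, as the last day of the first trimester". SAP 4.1.2 defines the infants' set (FASI) as "all infants born to women in the FASW who were potentially exposed to ocrelizumab during pregnancy".

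The safety sets follow by equation: "The safety analysis set of women (SAFW) will be the same as the FASW" (SAP 4.1.3) and "The safety analysis set of infants (SAFI) will be the same as the FASI" (SAP 4.1.4). SAP 4.8 and 4.8.2 run every AE summary on these two sets.

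Two other places describe the infant populations differently:

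- The primary estimand in SAP 4.4.1 labels its population FASI, but adds that the infant was not exposed beyond the first trimester. SAP 4.1.2 has no such condition.
- Protocol Section 6 carries no potential-exposure qualifier for infant safety: "The safety population for infants will include all infants of mothers in the FAS population". SAP Section 4 says that the SAP's analyses override the protocol's.

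SAP 4.2 adds: "Mothers and infants enrolled but excluded from the respective FAS will be listed".

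**The concern.** An exposure window suits the B-cell estimand, which asks about infants whose mothers were last dosed within stated limits. It is a poor criterion for a safety set, whose purpose is to account for everyone enrolled and exposed. Because the safety sets are defined by equation, the window governs the AE tables, the growth and ASQ-3 tables (SAP 4.6.1, 4.6.2) and, since it is built on the infants' safety set (SAFI), the vaccine-response set (SAP 4.1.5).

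The sharpest consequence concerns an infant exposed after Week 13. Protocol 3.3.2 regards placental transfer of IgG as significant from that point. If such an infant leaves SAFI while the mother stays in the women's safety set (SAFW), the infant tables lose a participant for a reason tied to exposure.

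**Working it through.** This is mainly a check of definitions, with date arithmetic to see who is affected.

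**1. The window.** SAP 4.1.1 gives 13 × 7 + 6 = 97, which reproduces. Taking 6 months as 182 days, the figure used in SAP 4.8.1, the window runs from day −182 to day 97 relative to the LMP. The criterion is exposure within the window. It neither requires the last dose to lie there nor bars a later one.

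**2. Late dosing on the usual schedule.** Protocol 1.2 gives a 24-week interval (168 days), and the protocol elsewhere speaks of 6-monthly infusions (182 days). Take a late dose on days 98 to 216, that is, from Week 14 to the end of Week 30 (30 × 7 + 6 = 216). The previous dose then falls on:

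- 168-day interval: 98 − 168 = −70 to 216 − 168 = 48
- 182-day interval: 98 − 182 = −84 to 216 − 182 = 34

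All of these days lie inside −182 to 97, so the woman stays in FASW and SAFW. She leaves only if the late dose was her first, or if the previous interval exceeded 98 + 182 = 280 days (late dose on day 98) up to 216 + 182 = 398 days (late dose on day 216).

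**3. Dosing between enrolment and birth.** Protocol 3.1.3 has such a woman discontinued from the study. An eligible woman already has an in-window dose, so she still meets FASW; no text removes her.

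**4. The definitions side by side.**

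| Case | Mother in SAFW | Infant in SAFI, by 4.1.2 | Infant in SAFI, by 4.4.1 |
|---|---|---|---|
| Last dose in window | yes | yes | yes |
| All doses more than 6 months before LMP | no | no | no |
| Dose after Week 13, none in window | no | no | no |
| Dose in window and again after Week 13 | yes | yes | no |

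Rows 2 and 3 are lost under either definition. In row 4 the two SAP descriptions of one set disagree.

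**5. Size.** The documents give no deviation rate. As an assumption, let 1 or 2 of the planned 33 women be outside the set: 1/33 = 3.0% and 2/33 = 6.1%. As an extreme case, suppose the only events of one type fell in those women. With Clopper-Pearson 95% limits (for zero events the upper limit is 1 − 0.025^(1/n)):

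- One woman: the table shows 0/32 (upper limit 10.9%) instead of 1/33 = 3.0% (0.1% to 15.8%).
- Two women: it shows 0/31 (upper limit 11.2%) instead of 2/33 = 6.1% (0.7% to 20.2%).

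**6. What the listings recover.** SAP 4.8.2 lists SAEs, AESIs, AEs leading to withdrawal, and deaths, and names no analysis set for that listing. The SAP 4.2 listing identifies who was excluded. No AE listing is planned for the remaining events, so a non-serious infection in an excluded infant would reach no planned AE table or listing.

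**The case against.** The strongest reply is that the affected group should be empty or nearly so. An out-of-window last exposure is an exclusion criterion (Protocol 4.1.2), in-window exposure must be documented (4.1.1), eligibility is confirmed before enrolment (4.5.1), and waivers are not allowed (9.2). The SAP 4.2 listing is a routine conditional output and does not show that exclusions are expected. The key AEs, all growth data (SAP 4.6.1) and pregnancy outcomes (SAP 4.8.6) are listed, and SAEs reach the sponsor individually. For women, equating the safety set with the full analysis set is also the protocol's own choice. All of this stands and keeps the priority low. It does not resolve the conflict between SAP 4.1.2 and 4.4.1 or supply the missing non-serious AEs.

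A reader might go further in three ways that the documents do not support:

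- **That any woman dosed after Week 13 drops out with her infant.** Step 2 shows that on the usual schedule she stays in SAFW. Only the infant is in doubt, and only through SAP 4.4.1.
- **That the excluded infants are in general the more exposed ones.** A last dose more than 6 months before the LMP is also out of window and means less exposure.
- **That SAFI drops every infant whose mother was dosed 3 to 6 months before the LMP.** Protocol 3.1 and SAP Section 2 do limit potential fetal exposure to under 3 months before the LMP or the first trimester, and Protocol 3.3.2 calls the 3-to-6-month women non-exposed. But the study title and objectives apply the potential-exposure wording to the whole population, the estimand reaches back 6 months, and SAP 4.4.5 and 4.8.2 require tables for the 3-to-6-month group. The qualifier is untidy, but the narrow reading fails.

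**Conclusion.** The point holds in a limited form. As written, the B-cell exposure window governs the safety tables. It removes an enrolled woman with no in-window dose together with her infant, and SAP 4.4.1 can remove an infant exposed after Week 13 whose mother remains. The loss is from the summary tables and, for AEs outside the listed categories, from planned AE output altogether; it is not a loss from all reporting. Whether the SAE and death listings would themselves be confined to the safety sets is not stated.

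The number affected is unknown and should be small. The figure of 1 to 2 of 33 is an assumption, as is reading 6 months as 182 days for the window. Priority: minor. The case for changing it is that the correction is nearly free.

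**What to change.** - **SAP 4.1.3 and 4.1.4:** define SAFW as all enrolled women (all ocrelizumab-exposed) and SAFI as all live-born infants of enrolled women, regardless of the exposure window. This also drops the potential-exposure qualifier that the protocol's infant safety population does not carry.
- **FASW and FASI:** keep them for the B-cell and PK endpoints.
- **SAP 4.1.5:** build the vaccine-response set (AIRI) on FASI, so that this secondary analysis population does not widen as a side effect.
- **SAP 4.1.2 and 4.4.1:** give FASI one definition that says explicitly whether exposure after the first trimester excludes the infant.
- **SAP 4.8.2:** add a category for a dose outside the protocol window to the exposure tables, shown when not empty. The three-interval split has no place for these participants.

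The cost is a few SAP sentences and no new data. Safety denominators may differ slightly from the full analysis sets. Exploratory analyses that default to the safety sets (SAP 4.6), including growth and ASQ-3, would gain the same few participants, which the SAP should state.
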